### **Primary Efficacy Analysis**

The primary outcome is the change in physical activity recorded with accelerometers between baseline and EoI. The variables to be analysed are minutes spent each week on light moderate and vigorous exercise as well as minutes spent sedentary and will be analysed using multiple linear regression. The model will have outcome as the dependent variable with baseline values as a covariate along with intervention group (Intervention/Control), and hospital as fixed effects.

Confounding variables to be assessed for importance are: Cognitive risk perception, Affective risk perception, Physical Activity self-efficacy, age, sex, surgery type (Colon or rectal surgery), Surgical intervention (e.g. laparoscopic or open surgery); stoma (Temporary (a loop ileostomy), permanent stoma or no stoma) and medical intervention (Chemotherapy or no chemotherapy).

### **Secondary Efficacy Analyses**

- SPAQ: All minutes of activity during the previous week will be summed up for analysis to provide a total minutes of activity in a week. In addition, the activities will be summed up separately for each week and analysed... Where no entries were made for a day, it will be assumed that there was no activity (0 minutes) in this category.
- FACT-C: The questionnaire consists of 5 subscales (Physical Well-being (PWB), Social/Family Well-being (SWB), Emotional Well-being (EWB), Functional Well-being (FWB), Additional Concerns (AC)). Composite scales are also calculated as described in the guidelines. As emotional well-being was not collected in this trial, composite scores including those questions were not created.
- FACIT-F: The questionnaire consists of 13 items and will be calculated as described in the guidelines.
- Activity Self-efficacy: If no more than 20% of the items are missing, a sum score will be created from all items in the questionnaire and used for analysis.

- EQ-5D: Physical domains will be analysed separately using logistic regression as described above. The health state will be analysed using ANCOVA as described above. In addition, the health utility score will be created and analysed.
- HADS: Two separate scores for anxiety and depression will be created and analysed.
- Risk perception: Three distinct scores will be created: Cognitive risk perception, affective risk perception and perceived severity as a sum of 2 questions each. Each score will only be created if both items are present. Scores will be analysed as described.
- Service use: This data will be analysed by the health economics team and is not part of this SAP.

## **Safety Analyses**

### **Adverse Events**

Adverse events (AE) will be coded with MedDRA 16.1. Where more than one diagnosis is present in the AE description, the AE will be split with all the descriptors kept the same for all diagnosis. Adverse events will be reported by primary System Organ Class (SOC) and Preferred Term (PT).

Subjects will be counted only once when calculating the incidence of AEs. An overview table will be created counting the number of adverse events by system organ class and preferred term.

Descriptors for Adverse events will be tabulated separately as described for categorical variables in section 8. The total number of AEs will be used as basis for tabulation.

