### **Serious Adverse Events**

Serious Adverse Events (SAE) will be reported with all other AEs as described in section 10.1. However, they will be reviewed for the trial report on a case by case basis by the PI.

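### Adverse events with several diagnoses are split into rows with copied descriptors, so on the natural reading one serious event can count more than once in the event-level descriptor tables

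*SAP*

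**What the plan says.** Four rules matter, all under Safety Analyses in the SAP.

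- **Splitting.** When a report names several diagnoses, "the AE will be split with all the descriptors kept the same for all diagnosis". One report with several diagnoses becomes several records with identical descriptor values.
- **Coded tables.** "An overview table will be created counting the number of adverse events by system organ class and preferred term". A separate rule covers incidence: "Subjects will be counted only once when calculating the incidence of AEs".
- **Descriptor tables.** "Descriptors for Adverse events will be tabulated separately as described for categorical variables in section 8", with the base given as "The total number of AEs will be used as basis for tabulation". The section referred to appears to be Summary of Study Data, which asks for frequencies and percentages of non-missing records.
- **Serious events.** "Serious Adverse Events (SAE) will be reported with all other AEs as described in section 10.1". In addition, "they will be reviewed for the trial report on a case by case basis by the PI".

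The SAP does not list the descriptors. It does not say whether the total number of adverse events is taken before or after the split. It gives no rule that ties split records back to the report they came from.

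Protocol section 6.7.7 defines a serious adverse event by what the event leads to: death, admission or a longer stay, or lasting or significant disability. A note adds events that the investigator judges to have significant clinical impact.

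**The concern.** Splitting by diagnosis is the normal way to obtain one coded term per record, and the table by system organ class and preferred term needs it. The difficulty comes when the same records feed the descriptor tables. Whether an event was serious is a property of the event. One admission recorded with three diagnoses is one serious event under the protocol's definition, but it becomes three serious records under the SAP.

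The number of serious events in each arm would then depend partly on how many diagnoses the reporter wrote on a form. With about 66 patients planned, 33 per arm, a few such reports could visibly change a per-arm table. Those tables will be read as a description of the safety of exercise classes for patients recovering from surgery, and they may be carried into the planning of the larger trial.

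**Working it through.** **Is there a figure to reproduce?** No. Neither document gives an expected or observed number of adverse events, so what follows is a counting identity with an illustration.

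**Do the existing rules prevent the repeat count?**

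1. The once-per-subject rule applies to incidence. The descriptor tables use events as their base, so the rule does not reach them.
2. Serious events follow the same reporting route as all others. No separate count of serious events is defined.
3. Case-by-case review of serious events informs the narrative. Nothing says that it corrects a table.
4. Percentages use non-missing records. Copied records are non-missing wherever the original was, so they enter both numerator and denominator.

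Nothing in the text prevents it.

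**Formula.** Let E be the number of reports and S the number that are serious. Let a be the extra rows created by splitting serious reports, and b the extra rows from non-serious reports. A report with k diagnoses adds k − 1 rows.

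- Counted per report: S / E.
- Counted after splitting: (S + a) / (E + a + b).

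The serious count rises by a whenever a > 0. The percentage rises only if the serious share of the added rows, a/(a + b), exceeds S/E. It is unchanged if the two are equal and falls if it is smaller.

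**Illustration.** Assumed, not from the documents: E = 40 and S = 6, so the per-report figure is 6/40 = 15.0%.

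| Reports with several diagnoses | a | b | After splitting |
|---|---|---|---|
| One serious, two diagnoses | 1 | 0 | 7/41 = 17.1% |
| One serious, three diagnoses | 2 | 0 | 8/42 = 19.0% |
| Two serious, three each | 4 | 0 | 10/44 = 22.7% |
| Three serious, three each | 6 | 0 | 12/46 = 26.1% |
| Ten non-serious, two each | 0 | 10 | 6/50 = 12.0% |
| Half of each kind, two each | 3 | 17 | 9/60 = 15.0% |

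In the last row the percentage is right, but the serious count is 9 instead of 6.

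**If the base is taken before the split.** If both rows and base are unsplit, the table shows 6/40 and there is no problem. If rows are split but the base is not, the second line of the table gives 8/40 = 20.0% serious and 34/40 = 85.0% non-serious. These sum to 105.0%, so that combination cannot be intended.

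**Subject-level incidence.** A patient with one report split into three rows still counts once. This figure does not change.

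**The case against.** The best reply is that the unit of counting is a choice. Once each diagnosis is its own record, tabulating descriptors on those records keeps every safety table on one denominator. Counting per report has its own arbitrary element: three diagnoses on one form count once, while the same three on separate forms count three times. The split rule treats those two cases alike. The tables are also descriptive, no stopping rule depends on them, and no listed objective is a safety comparison.

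Much of this stands. It limits the importance of the point and shows that the remedy is not free. It does not settle the matter for seriousness, because the protocol's listed criteria attach to the event and its outcome. Copying that label to each diagnosis asserts something the reporter may not have meant.

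A reader might also infer more than the text supports:

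- **That severity and relatedness tables are affected.** The SAP names no descriptors, and neither safety section mentions severity grading or relatedness. Seriousness is a fair inference; the others are not documented.
- **That multiple counting is certain.** The SAP does not say that the total is taken after the split. That is the natural reading of the order of the rules, but not a stated one.
- **That the serious percentage is always inflated.** The last two lines of the table show otherwise.
- **That admissions are the events most likely to carry several diagnoses.** This is plausible, but the documents give no basis for it.

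**Conclusion.** The point holds in limited form. On the natural reading, split first and then tabulate, the SAP counts one reported event once per diagnosis in its event-level descriptor tables. The number of serious events in an arm is inflated whenever a serious report lists more than one diagnosis, while the percentage may rise, fall or stay the same.

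This rests on two assumptions: that the total number of adverse events is taken after splitting, and that seriousness is among the tabulated descriptors. The real size is unknown because no event counts are given, and the figures above show only how the count behaves.

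The documents do not support reading this as an error in splitting itself, in the incidence of adverse events by subject, or in any efficacy result. It is a minor point, worth correcting because the correction is small.

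**What to change.** Amend the SAP's Adverse Events section as follows.

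1. Keep an identifier of the original report on every split row.
2. Use split rows only for the tables by system organ class and preferred term.
3. Name the descriptors. Tabulate seriousness and any others recorded once per original report, and state that denominator.
4. Give the number and percentage of randomised patients in each arm with at least one adverse event and with at least one serious adverse event. The once-per-subject rule already covers part of this; an explicit line for serious events is what is missing.

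The cost is one variable and a few lines of text. There are two small drawbacks. Descriptor totals will no longer match the totals in the coded tables, so a footnote must explain the two denominators. The per-report count will also still depend on how events were divided between forms; the patient-level counts in item 4 are free of that dependence.

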### **Serious Adverse Events**

Serious Adverse Events (SAE) will be reported with all other AEs as described in section 10.1. However, they will be reviewed for the trial report on a case by case basis by the PI.

## **Reporting Conventions**

P-values  $\geq 0.001$  will be reported to 3 decimal places; p-values less than 0.001 will be reported as “<0.001”. The mean, standard deviation, and any other statistics other than quantiles, will be reported to one decimal place greater than the original data. Quantiles, such as median, or minimum and maximum will use the same number of decimal places as the original data. Estimated parameters, not on the same scale as raw observations (e.g. regression coefficients) will be reported to 3 significant figures.

## **Technical Details**

All analysis will be performed using SAS 9.3. All data, analysis programs and output will be kept on the Mackenzie Server and backed up according to the internal IT SOPs.

Analysis programs will be required to run without errors or warnings. The analysis programs for outcomes will be reviewed by a second statistician, and any irregularities within the programs will be investigated and fixed and date of finalised analysis programs will be signed and recorded.
